### 8.2 Performance Endpoints

All performance endpoints will be summarized by counts and percentages.

Device success is based on procedure data only. It will be evaluated for the ITT and AT cohorts at the time of the patient's exit from the cardiac catheterization laboratory.

The procedure success endpoint will be assessed for the AT cohort. The endpoint and its components will be assessed at the index procedure hospital discharge.

The clinical success endpoint at 30 days will be summarized by counts and percentages for the AT cohort. DMC adjudicated data will be used for MAEs. The endpoint and its components will be assessed at the 1 month follow-up interval.

### 8.3 FDA Endpoints

FDA Device Success, FDA Procedural Success, and FDA Individual Patient Success will be summarized by counts and percentages for the overall success variable and each of their individual components.

### 8.4 Additional Analysis

 Edwards	Revision Date: April 1, 2019		Rev	3.0	For Use Only by Affiliates of Edwards Lifesciences	Page 17 of 18
	Title	Statistical Analysis Plan for FORMA EFS				

#### 8.4.1 Echocardiographic parameters

Echocardiographic data will be provided by a core laboratory. TTE parameters will be assessed at baseline, discharge, 30 days, 6 months, 1 year and annually until 3 years post procedure. TEE parameters will be assessed at the start and the end of the initial implant procedure. The change from baseline for selected items will be presented as a shift from baseline for each of the pre-specified follow-up periods (paired analysis). Patients that are missing baseline or follow-up values will be excluded from the paired analysis. Patients that undergo any type of repair or replacement procedure for the tricuspid valve will be excluded from analysis at the time of the reintervention.

#### 8.4.2 Clinical parameters

Re-hospitalization rates will be assessed at 1 month, 6 months and annually up to 3 years.

Time to first Heart Failure Re-hospitalization will be assessed via the Kaplan-Meier method for the AT cohort. In addition, the HF Re-hospitalization rate (number of HF Re-hospitalization per patient-year) will be analyzed.

Patient specific functional status (NYHA Class), exercise capacity (6MWD), and quality of life (SF-12 and KCCQ) metrics will be assessed at baseline, 1 month, 6 months, and 1 year and beyond.

Patients that undergo any type of repair or replacement procedure for the tricuspid valve will be excluded from analysis at the time of the reintervention. Only data up to the point of reintervention will be used.

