8.10 PATIENT STUDY COMPLETION

Study patients complete and exit the study when no additional follow-up visits, procedures, or data collection are required. Patients will then continue to be followed by their primary health care provider as required.

A patient will also be exited from the study in the following instances:

- Patient signs informed consent form, is deemed eligible but does not undergo the study procedure
- Patient has study procedure attempted (at least skin incision to introduce the FORMA System) and does not have the investigational device implanted (will exit study at the 1 month follow up visit)
- If the study device is explanted, the patient will be followed for 30 days after the explant procedure for safety evaluations only, and will be exited from the study at that point. If one or more ongoing adverse event(s) related to the explant procedure is unresolved 30 days after the explant, the patient will remain in the study until the adverse event(s) have been resolved, or 180 days post explant, whichever comes first
- Patient is lost-to-follow-up
- Patient withdraws participation from the study or is withdrawn from the study
- Patient expiration

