## 2. STUDY DESIGN

### 2.1 Study Objectives

The objectives of this early feasibility study are to:

- Evaluate the safety and function of the Edwards FORMA System
- Provide guidance for future clinical study designs utilizing the Edwards FORMA System
- Provide guidance for future FORMA System development efforts.

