**3.3.3 FDA Individual Patient Success (at 6-months & 1 year): Effectiveness**

- Device Success and all of the following:
  - a) No re-hospitalizations or re-interventions for the underlying condition (e.g. HF or TR)
  - b) Improvement vs. baseline in symptoms (e.g. NYHA Class improves from baseline)
  - c) Improvement vs. baseline in functional status (e.g. 6MWT improves from baseline)
  - d) Improvement vs. baseline in QoL (e.g. SF-12, KCCQ improves from baseline)

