## 5. DEFINITIONS

### 5.1 Analysis Dates and Days

- Reference Start Date and Day 0

The reference start date is defined to be the date of the index procedure. The index procedure is defined as the time the first interventional access-related puncture (arterial) is established.

The reference start date is considered to be day 0.

- Last Participation Date

The Last Participation Date is defined as the last date the patient is seen (e.g. maximum of the last date of procedure date, discharge date, follow-up visit date, exit date, adverse event date, and laboratory test date).

- Last Participation Day

Last Participation Day = Last Participation Date – Reference Start Date

Note: Last Participation Day is used as censor day for Kaplan-Meier analysis.

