## 6. DATA AND ANALYSIS CONVENTIONS

### 6.1 General Conventions

- For continuous variables, summary statistics will include number of observations, mean, median, standard deviation, minimum, maximum, and 95% confidence intervals (based on normal distribution) per table shells. Nonparametric techniques may be used if the data does not meet the assumptions of parametric tests.
- For ordinal data, the count and percentage of patients will be presented.
- For categorical and qualitative variables, summary statistics will include number of observations, percentage, and 95% Clopper-Pearson confidence intervals per table shells. In general, the denominator for the percentage calculation will be based on total number of patients with evaluable data for a specified time point unless otherwise specified. Patients with missing data will be excluded from the denominator.
- Survival analysis techniques will be used to analyze the time-to-event variables. Summaries will include the number of patients at risk, number of events, number of patients with the event, and Kaplan-Meier estimates at given time points. Patients without events will be censored at their last known event-free time point. If this event-free time point occurs after the analysis time point, the days to event variable will be set equal to the analysis time point so that the patient will be included in the analysis. For patients who did not have an event or early withdrawal and have not yet completed the analysis visit, they will be censored at their last participation date. Standard errors will be calculated using Greenwood's formula and SAS defaults will be used for confidence bands and transformations on  $S(t)$  for the confidence limits. Kaplan-Meier event rate plots will be presented via the cumulative hazard rate plotted against the days from implantation.

- [REDACTED]

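### Kaplan-Meier for first HF re-hospitalization censors deaths, so 1-KM is at or above the cumulative incidence; report the competing-risk estimate beside it (minor)

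*SAP*

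**What the plan says.** The estimator is named in SAP 8.4.2: "Time to first Heart Failure Re-hospitalization will be assessed via the Kaplan-Meier method for the AT cohort". The same section plans an HF re-hospitalization rate per patient-year and, more generally, "Re-hospitalization rates will be assessed at 1 month, 6 months and annually up to 3 years".

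The censoring rule is general. SAP 6.1 says "Patients without events will be censored at their last known event-free time point", and SAP 5.1 adds that "Last Participation Day is used as censor day for Kaplan-Meier analysis". The last participation date is the latest date on which the patient was seen, and it includes the exit date.

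Neither definition of an HF hospitalization in Protocol 18 includes death. Protocol 8.10 lists "Patient expiration" among the study exits. So a patient who dies without an HF admission is a patient without the event, and is censored.

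No readable text treats death as a competing event, asks for a cumulative incidence function, or defines a composite of death and HF admission. One bullet at the end of SAP 6.1 is blacked out and the table shells are not supplied, so a convention could sit there.

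**The concern.** Kaplan-Meier treats a censored patient as someone who stays at risk and will have the event at the same rate as those still followed. That can be defended for a patient who is lost to follow-up. It cannot hold for a patient who has died. The quantity 1-KM then describes a setting in which nobody dies, not the fraction of implanted patients who have a first HF admission.

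The stake is interpretation. One study objective is to "Provide guidance for future clinical study designs utilizing the Edwards FORMA System", and follow-up runs to 3 years, where the gap is widest. A designer who takes the cause-specific HF hazard and adds a separate death hazard is not misled. A designer who takes the 3-year curve as the proportion of patients re-hospitalized may plan on too high a figure.

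**Working it through.** **Inputs.** From the documents: 60 enrolled (SAP 2.3), so at most 60 in the AT cohort; follow-up to 3 years; Kaplan-Meier with every event-free patient censored. The documents state no HF admission rate, death rate or event count, so there is no planned figure to reproduce. Every rate and count below is an assumption.

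**Step 1: the condition, without a hazard model.** Take 60 AT patients with no censoring other than death and end of study, 20 first HF admissions and 14 deaths without one. Aalen-Johansen equals the observed share, 20/60 = 33.3%, in any order of events. 1-KM depends on the order:

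- All deaths after the last admission: 1-KM = 20/60 = 33.3%, no excess.
- Deaths and admissions evenly interleaved: 1-KM = 38.9%.
- All deaths before the first admission: 1-KM = 20/(60-14) = 20/46 = 43.5%.

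With 7, 3 or 1 interleaved deaths instead of 14, 1-KM is 35.8%, 34.3% or 33.7%. The excess is never negative. It appears only when a death without admission precedes a later first admission, and it shrinks quickly when such deaths are few.

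**Step 2: size over time, under constant independent hazards.** Let F be 1-KM at 3 years and M the net 3-year death risk. Set h = -ln(1-F), d = -ln(1-M), and let t be the fraction of 3 years elapsed.

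- 1-KM(t) = 1 - exp(-ht)
- Cumulative incidence(t) = h/(h+d) × [1 - exp(-(h+d)t)]
- Actual death before any admission(t) = d/(h+d) × [1 - exp(-(h+d)t)]

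Worked case, F = 40% and M = 30%, at t = 1: h = 0.511, d = 0.357, h/(h+d) = 0.589, and 1 - exp(-(h+d)) = 1 - 0.6 × 0.7 = 0.58. Cumulative incidence = 0.589 × 0.58 = 34.2%, and 23.8% die before any admission. The excess is 40.0 - 34.15 = 5.85 points.

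3-year cumulative incidence, with actual death before admission in brackets, in %:

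| 1-KM at 3 years | M = 10% | M = 20% | M = 30% | M = 40% |
|---|---|---|---|---|
| 30% | 28.6 (8.4) | 27.1 (16.9) | 25.5 (25.5) | 23.8 (34.2) |
| 40% | 38.1 (7.9) | 36.2 (15.8) | 34.2 (23.8) | 32.0 (32.0) |
| 50% | 47.7 (7.3) | 45.4 (14.6) | 42.9 (22.1) | 40.3 (29.7) |

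Range of 1-KM minus cumulative incidence over this grid:

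| Time | Excess, points |
|---|---|
| 6 months | 0.05-0.44 |
| 1 year | 0.19-1.60 |
| 2 years | 0.70-5.23 |
| 3 years | 1.44-9.70 |

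**Step 3: against sampling error.** At 40% and N = 60 the 95% half-width is 1.96 × √(0.4 × 0.6/60) = 12.4 points. Every value in the grid is smaller.

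**The case against.** **It is a reporting preference, not an error.** SAP 8.4.2 does not say that the curve estimates the share of patients re-hospitalized. A death-censored Kaplan-Meier curve is standard, its cause-specific hazard is valid, and nothing is decided on it. This stands, and it is why the point is minor.

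**Other planned outputs already help.** The patient-year HF rate is not read as a proportion. FDA Device Success (SAP 3.3.1) has being alive as a component at each follow-up visit, and SAP 8.3 summarizes each component, so mortality will be visible. Protocol 18 classifies hospitalizations by cause, so HF-specific visit rates could be derived. SAP 6.1 also reports the number of patients with the event. These weaken the harm, but none gives the share with a first HF admission:

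- The patient-year rate is not a share.
- The alive component does not separate deaths with and without an earlier HF admission.
- The visit rates are not specified as HF-only and name no estimator.
- The raw count gives the share only if follow-up is complete.
- The re-hospitalization component of FDA Individual Patient Success (SAP 3.3.3) mixes HF or TR admissions with re-interventions and stops at 1 year.

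**A reader might infer that 1-KM can only err high.** That holds against the Aalen-Johansen estimate, but against the true share it holds only if other censoring is non-informative. Data stop at tricuspid reintervention (SAP 8.4.2), and explanted and withdrawn patients leave the study (Protocol 8.10). Suppose that of 60 patients 10 exit early for such reasons, 2 then die unadmitted, and 12 of the remaining 48 are admitted: 1-KM = 12/48 = 25.0%. If 4 of the 10 exits are later admitted, the true share is 16/60 = 26.7%. 1-KM is then too low, and Aalen-Johansen at 12/50 = 24.0% is lower still. This objection is right, and the conclusion is limited accordingly.

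**A reader might also add the plotting convention to the size.** SAP 6.1 says "Kaplan-Meier event rate plots will be presented via the cumulative hazard rate plotted against the days from implantation". At a 1-KM of 40% the cumulative hazard is 0.511, 11.1 points higher, but that gap is a matter of scale and would exist with no deaths. It is a separate presentation point and is not counted here.

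**The top of the range is demanding.** An excess of 9.7 points needs 29.7% of patients to die without any HF admission, while entry excludes life expectancy under 12 months, significant frailty and severe RV dysfunction. That is fair. Equally, the documents give no rate that would narrow the range.

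**Conclusion.** The point holds as a minor one. On the readable text, AT patients who die without an HF admission are censored. 1-KM is then never below the Aalen-Johansen cumulative incidence and exceeds it whenever such a death precedes a later first admission. It overstates the share of patients re-hospitalized provided that censoring for withdrawal, explant exit and reintervention is non-informative.

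The plausible excess is negligible at 6 months, at most 1.6 points at 1 year, and about 1.4-9.7 points at 3 years. This rests on assumed constant, independent hazards and assumed rates. It is below the sampling half-width throughout, but the Kaplan-Meier confidence interval does not reflect it.

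The documents do not support reading this as a flaw in the study's main conclusions. The 30-day MAE endpoint, the performance endpoints and the cause-specific hazard are untouched. Nor can it be said that the plan has no competing-risk convention at all, because of the blacked-out bullet in SAP 6.1.

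**What to change.** In SAP 8.4.2, replace the Kaplan-Meier sentence with wording such as: *First HF re-hospitalization (AT cohort) will be reported and plotted as Aalen-Johansen cumulative incidence with death as the competing event, with 95% CI at 30 days, 6 months and 1, 2 and 3 years. The Kaplan-Meier estimate will be shown beside it, labelled as death-censored.* Leave the patient-year rate and all 30-day endpoints as they are.

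The cost is two sentences, one changed table and one changed figure, from data already collected. Keeping Kaplan-Meier preserves comparability with rates published as 1-KM. The downside is that two estimates of one outcome need clear labels, and the late intervals stay wide at 60 patients. The change does not deal with informative exits for explant, reintervention or withdrawal, so the number of patients censored for each reason is worth stating with the result.

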#### 8.4.3 Additional Safety Analysis

Site-reported adverse events (AEs) and serious adverse events (SAEs) will be summarized by early events ( $\leq 30$  days) and late events ( $> 30$  days) for the ITT cohort. In addition, a listing of all the AEs and SAEs for the entire study population will be provided.

#### 8.4.4 Sub-group Analysis

Subgroup analysis by enrollment (i.e., patients enrolled prior to Protocol Rev L vs. the remaining patients) will be performed, whenever applicable.

 Edwards	Revision Date: April 1, 2019		Rev	3.0	For Use Only by Affiliates of Edwards Lifesciences	Page 18 of 18
	Title	Statistical Analysis Plan for FORMA EFS				

## 9. CHANGES FROM PROTOCOL SPECIFIED ANALYSES

Protocol version M had changed the definitions of per protocol population, in addition to that, the wording on echocardiographic parameters Section had also changed. This new version of the SAP incorporates those changes to be consistent with the protocol Rev M. The wording of “Rev L and after” in this version replaced “Rev L” in SAP 2.0 will help clarify the patient population available for analysis.

